### Missing Data

Given that our trial follow-up is through administrative health care data held at ICES, we anticipate no missing data for our outcomes unless a patient emigrated from Ontario during follow-up (anticipated in <0.5%), which will be treated as a censoring event in the primary analysis.

From previous work, we anticipate a small amount of missing data on some baseline characteristics. We will recode missing data on rural status as urban, missing data on race as Caucasian, and missing data on the modified Charlson comorbidity index as 2 (the minimum value associated with kidney failure). If there is <10% missing data on baseline serum albumin, we will use simple imputation; if there is between 10% and 40% missing, we will use multiple imputation; if there is >40% missing, we will exclude serum albumin from the adjusted analyses.

### Harms

As described in prior studies (summarized in the protocol), the MyTEMP intervention is well tolerated by patients. It was deemed a minimal risk to patients by the Research Ethics Review Boards which approved MyTEMP (further details in the protocol). There was a waiver of patient consent for enrollment into MyTEMP, and patients were notified through posters and letters about their dialysis center's allocation. A patient or their nephrologist retained the option to opt out of the random allocation (ie, receipt of the treatment); however, patients could not opt out of data collection of the primary analysis as data are obtained as secondary use of routinely collected data. There are no prior data to suggest the intervention will increase the risk of our primary or secondary outcomes compared with the control group (although our hypothesis testing approach will examine for this possibility). We have undertaken a separate independent substudy in

a small set of centers to confirm there are no large between-group differences on patient-reported symptoms (eg, feeling cold on dialysis). We are also linking some electronic dialysis medical records to the ICES databases, to confirm in an observational cohort that the intervention is not associated with an altered risk of missed dialysis treatments or coming off hemodialysis treatments early.

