## Protocol Summary

**Objective:** To report descriptive symptomology statistics of a group of patients receiving personalized dialysate temperatures (0.5°C-0.9°C below patients' body temperature) and a group of patients receiving usual dialysate temperature of 36.5°C.

**Settings:** Ten hemodialysis centres across the London Health Sciences Centre renal program that are participating in the MyTEMP clinical trial. Five centres are allocated to personalized reduced dialysate temperature and five centres are allocated to control dialysate temperature.

**Patients:** Consenting adults at least 18 years old, with no communication impairment (blind/deaf), and reasonable ability to speak and understand English.

**Interventions:** MyTEMP PRO will be utilizing treatment allocations from the MyTEMP parent randomized trial.

**Measurements:** Patients will be asked to: 1) complete the Edmonton Symptom Assessment System (revised) Renal (ESASr: Renal) questionnaire using a visual analog scale; 2) how cold they feel while on dialysis; 3) severity of muscle cramps; 4) headaches while on hemodialysis; 5) record their self-rated health; 6) record if they have missed a session in the last month; and 7) record their average amount of time required to recover from their dialysis session (i.e. return to normal duties). We will capture this information electronically using a website accessed on a tablet.

**Outcomes:** ESASr: Renal item scores, self-rated temperature, self-rated cramp severity, self-rated health, missed sessions, and time to recover following dialysis.

**Planned analysis:** Descriptive statistics will be reported.

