## Self-Rated Temperature

Measuring how cold a patient feels on dialysis is integral to understanding the systemic effects of personalized dialysate temperature. There have been previous reports that have shown that 20% of patients report feeling cold, and another study has reported 2 out of 10 patients shivering on lower dialysate temperatures of 35.0°C (18,42). Gathering further information in this sub-study would provide further insight into the differentiation in temperature sensations between personalized dialysate temperatures and standard 36.5°C.

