## **Objective**

Report descriptive statistics for both intervention and control arms of MyTEMP on the symptoms of patients through the use of the Edmonton Symptom Assessment System (Revised): Renal. Descriptive statistics will also be reported for time to recover following dialysis, and self-rated health.

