## Methods

### Study Design

MyTEMP PRO is a nested patient-level cross-sectional qualitative and registry-based study that will gather patient reported outcome (PRO) data from the 10 centres participating in the MyTEMP trial (~600 patients).

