### **Harms and Benefits:**

There are no expected harms in the completion of the MyTEMP PRO questionnaire; however, as with any questionnaire study, there is a minimal risk of privacy breach and some participants may feel uncomfortable completing questions related to their symptomology. Should patients feel uncomfortable, the participant will not be required to answer the question. The patients will be made aware that their survey responses are being used to assess the impact of dialysis temperature, not to be used to influence their clinical care. Patients will be asked to communicate symptom concerns to their healthcare team.

The results of MyTEMP PRO will provide further information on potential benefits of personalized dialysate. Because no statistical comparisons are being made in this study, MyTEMP PRO will set a foundation for future patient-reported outcome studies investigating personalized dialysate temperatures.

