## **Statistical Analysis:**

We will report descriptive statistics for MyTEMP PRO outcomes for each arm of MyTEMP. This will include the mean, standard deviation, median, and interquartile ranges for each individual ESASr: Renal item, feeling of coldness, cramp severity, missed sessions, self-rated health and time to recover following dialysis.

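### The SAP gives the symptom substudy the purpose of confirming no large between-group differences, but the substudy plans only per-arm descriptive statistics, which cannot by themselves confirm that

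*Combined protocol and SAP*

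**What the plan says.** The SAP, under Harms, describes a separate substudy in a small set of centres, undertaken to "confirm there are no large between-group differences on patient-reported symptoms (eg, feeling cold on dialysis"). The sentence after it describes a second check: linked electronic dialysis records will be used to look at missed treatments and treatments stopped early. The corrigendum to the SAP changes three other items and leaves this section as it was.

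The substudy protocol (MyTEMP PRO) sets a different task:

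- Objective: "Report descriptive statistics for both intervention and control arms of MyTEMP on the symptoms of patients".
- Statistical Analysis: "We will report descriptive statistics for MyTEMP PRO outcomes for each arm of MyTEMP". The statistics listed are the mean, SD, median and interquartile range.
- Harms and Benefits: "Because no statistical comparisons are being made in this study", the survey is to lay a foundation for future studies.
- Protocol Summary, Settings: "Five centres are allocated to personalized reduced dialysate temperature and five centres are allocated to control dialysate temperature".
- Study Design: "data from the 10 centres participating in the MyTEMP trial (~600 patients").
- Sample Size: recruit as many patients as possible. No precision target is given.

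The final protocol (Discussion, third limitation) warns that self-report is of doubtful reliability when patients know their dialysate temperature, and that power with a subset of centres is limited.

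**The concern.** Confirming that no large difference exists is a claim about which differences the data rule out. It needs an estimate of the between-arm difference, an interval around it, and some idea of what counts as large. The substudy plans none of these, so a reader of the two arm summaries would have to judge the matter by eye.

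A reader could go further and build an interval from the reported means, SDs and numbers. That interval would treat patients as independent, although the temperature protocol was allocated by centre, with five centres per arm. It would be too narrow and would reassure too much.

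What is at stake is the symptom part of the tolerability statement. The final protocol says the administrative data hold no symptom information, and the record linkage covers missed and shortened treatments, not symptoms. This survey is therefore the only source of symptom data that the documents describe.

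**Working it through.** **Text against text.** The SAP's purpose is a between-group conclusion (absence of large differences). The substudy's output is one set of summaries per arm, with comparison expressly disclaimed. Both are current text. No step in either document leads from the output to the conclusion.

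**Illustration of what an interval would look like.** The documents state no figure for this, so there is nothing to reproduce, and the mismatch does not depend on the calculation.

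Inputs from the substudy protocol: 10 centres, 5 per arm (Protocol Summary); about 600 patients (Study Design), so about 300 per arm and 60 per centre if centres are equal. The 600 are patients, not expected responders, and no response rate is given.

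Assumptions: all respond; equal centres; intraclass correlation (ICC) 0.01, 0.05 or 0.10; SD of 2 to 3 points on a 0 to 10 item.

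Design effect: DE = 1 + (m - 1) x ICC, with m = 60.
Standard error of the difference in SD units: SE = sqrt(2 x DE / n), with n = 300 per arm.
Half-width of the 95% interval: t(0.975, 8 df) x SE = 2.306 x SE, with 8 df from 10 centres minus 2 arms.

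| ICC | DE | SE | Half-width (SD) |
|---|---|---|---|
| 0.01 | 1.59 | 0.103 | 0.237 |
| 0.05 | 3.95 | 0.162 | 0.374 |
| 0.10 | 6.90 | 0.214 | 0.495 |

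Ignoring centres: 1.96 x sqrt(2/300) = 0.160 SD. The interval that allows for centres is about 1.5 to 3 times as wide (0.237/0.160 = 1.5; 0.495/0.160 = 3.1).

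In points on a 0 to 10 item, the range runs from 0.237 x 2 = 0.47 to 0.495 x 3 = 1.48.

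Sensitivity:

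- 300 responders in all (assumed; m = 30, n = 150 per arm): half-widths 0.302, 0.417 and 0.526 SD.
- 600 responders in unequal centres (assumed 20, 30, 50, 80 and 120 per arm), using unweighted centre means, with variance per arm = sum of (ICC + (1 - ICC)/m_i) / 25: half-widths 0.271, 0.396 and 0.510 SD.

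Example: arm means 0.2 SD apart, 600 responders, equal centres. Ignoring centres, the interval is 0.2 -/+ 0.160 = 0.04 to 0.36 SD. Allowing for centres, it is -0.04 to 0.44, -0.17 to 0.57 or -0.29 to 0.69 SD at the three ICCs. The first appears to exclude a difference of 0.4 SD; none of the others does.

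**The case against.** The strongest reply is that this is a mismatch of wording rather than a flawed analysis. The substudy protocol is consistently descriptive and makes no claim of absence. The SAP sentence is background about a separate study, states a purpose rather than a planned conclusion, and specifies no analysis. The limits of power and of unblinded self-report are already disclosed in the final protocol. All of this stands and keeps the point small. It does not remove it: the disclosed caveats make the word confirm harder to support, and they supply no estimate.

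A second reply is that large differences are just what a sample of this size can speak to. That is partly right. With an observed difference near zero and the assumptions above, differences beyond about 1.5 points of 10 could be excluded, but only if the interval is reported.

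A reader might also infer more than the documents support:

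- *That the substudy itself sets comparative aims.* Self-Rated Temperature hopes to "provide further insight into the differentiation in temperature sensations between personalized dialysate temperatures" and the standard temperature, and Harms and Benefits would tell patients that "their survey responses are being used to assess the impact of dialysis temperature". The first is background on why coldness is asked about and is compatible with description. The second goes on to say that answers will not influence clinical care, and the same section then disclaims comparison. The stated Objective is descriptive.
- *That tolerability is otherwise unchecked.* The record linkage in SAP Harms is a separate check, although it does not cover symptoms.
- *That the final report will assert absence of a difference.* The SAP does not say so.
- *That no comparative plan exists.* The compilation holds one substudy protocol, approved in August 2019; the SAP was submitted in April 2021. A later substudy analysis plan cannot be excluded.

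**Conclusion.** The point holds as a minor inconsistency. Followed as written, the substudy can describe symptoms by arm but cannot by itself confirm that no large between-group difference exists, which is the purpose the SAP gives it. This conclusion rests on the text alone.

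The half-width of 0.24 to 0.50 SD is an illustration. It depends on the assumed ICC, equal centres and response by all of the roughly 600 patients, and it widens with fewer responders. It shows why an interval that ignores centres would mislead, not that the survey is uninformative. The primary, key secondary and other tested outcomes of the main trial are unaffected.

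**What to change.** Either change is enough.

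1. Reword the sentence in SAP Harms to say that the substudy describes patient-reported symptoms in each arm and does not confirm the absence of a difference. This is certain to be feasible and costs one text edit.

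2. If centre is stored with each response, report for each symptom item the between-arm difference with a 95% interval from the ten centre means (t on 8 df, no p-values), and state which differences the interval excludes. Label any threshold for a large difference that was set after results were seen as post hoc; the SAP already speaks of the survey as undertaken. The text available does not say whether centre is stored: Data Linkage says only that no participant identifiers are collected, and reporting by arm does not by itself require centre to be kept.

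The second option costs one calculation per item and notification of the research ethics board, which the substudy's Protocol Amendments section requires for any change. It needs no new data or patients. Its intervals will be wide and cover sampling error only. They do not address unblinded self-report (final protocol, Discussion; substudy, Blinding) or voluntary participation (substudy, Recruitment), and the text should say so.

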### Statistical Software

The primary analyses will be performed in SAS software version 9.4 (NC, Cary). We may use additional software (eg, R Project, STAN or WinBUGS) for some analyses (eg, Bayesian analysis).

### Trial Status

Eligible hemodialysis centers in Ontario were randomized on February 1, 2017. Centers began delivering the intervention on April 3, 2017. The last day of follow-up is March 31, 2021. Eligible patients receiving in-center hemodialysis between April 3, 2017, and March 1, 2021, will be included in the analysis.

### Discussion

We designed a pragmatic, cluster-randomized registry trial to compare the effect of using a personalized, temperature-reduced dialysate protocol versus a fixed dialysate temperature of 36.5°C on the rate of cardiovascular-related mortality and hospitalizations. This work provides a comprehensive outline of the analytic plan for the MyTEMP trial. We discussed the methods used for our prespecified primary, key secondary, and other secondary outcomes. We also provided details on additional analyses, which will be used to assess the robustness of the findings in our primary analysis. We hope this article will aid in the interpretation of MyTEMP and the design and analysis of other hemodialysis cluster-randomized trials in the future.

### Ethics Approval

The Health Sciences Research Ethics Board at Western University centrally approved the research ethics application for Ontario through the Streamlined Research Ethics Review System managed by Clinical Trials Ontario (Application Number: CTO-0736). The use of the data for the ICES portion of the project is authorized under section 45 of Ontario's Personal Health Information Protection Act and does not require review by a Research Ethics Board.

### Consent to Participate

The Research Ethics Board approved our application with alteration to the informed consent process as described in the protocol.

### Consent for Publication

Consent for publication was obtained from all authors.

## Availability of Data and Materials

The ICES Analyst and Scientist involved in the study will have access to the trial data obtained through ICES. The data set from this study is held securely in coded form at ICES. While legal data sharing agreements between ICES and data providers (eg, health care organizations and government) prohibit ICES from making the data set publicly available, access may be granted to those who meet prespecified criteria for confidential access, available at [www.ices.on.ca/DAS](http://www.ices.on.ca/DAS) (e-mail: [contact]). The full data set creation plan and underlying analytic code may be available from the authors upon request, understanding that the computer programs may rely upon coding templates or macros unique to ICES and are therefore either inaccessible or may require modification. The study investigators will have access to the trial data collected outside of ICES. These data will not be available to the public.

## Declaration of Conflicting Interests

The author(s) declared the following potential conflicts of interest with respect to the research, authorship, and/or publication of this article: [name] has received consulting fees from Baxter Healthcare and Amgen. [name] is the owner of Oliver Medical Management Inc, which licenses Dialysis Management Analysis and Reporting System software. He has received honoraria for speaking from Baxter Healthcare and participated on advisory boards for Janssen and Amgen. [name] has received unrestricted research support from Baxter. The other authors declare no potential conflicts of interest to disclose.

## Funding

The author(s) disclosed receipt of the following financial support for the research, authorship, and/or publication of this article: We received funding for the Major Outcomes with Personalized Dialysate TEMPerature (MyTEMP) trial from the Lawson Health Research Institute, the Ontario Renal Network, Dialysis Clinic Inc, the Heart and Stroke Foundation of Canada, and the Canadian Institutes of Health Research (CIHR). Funding is also provided by the Ontario Strategy for Patient-Oriented Research SUPPORT Unit, which is supported by the CIHR and the Province of Ontario. This work is supported through a CIHR SPOR Innovative Clinical Trial Multi-Year Grant (Grant number: MYG-151209). [name] is supported by the Allied Health Doctoral Fellowship from the Kidney Foundation of Canada, Michael DeGroote Scholarship, and CIHR Doctoral Award. [name] is supported by the [name] Chair in Hemodialysis Innovation. [name] is supported by a Tier 1 Canada Research Chair in Perioperative Medicine and the McMaster University/Hamilton Health Sciences Chair in Perioperative Care. [name] is supported by the Jindal Research Chair for the Prevention of Kidney Disease. [name] is supported by the [name] Chair in Kidney Analytics and a Clinician Investigator Award from the CIHR. ICES is funded by an annual grant from the Ontario Ministry of Health and Long-Term Care.

## Data Monitoring

The Data Safety Monitoring Board (DSMB) (Drs [name], [name], and [name]) are experts in clinical trials and hemodialysis. The DSMB reviewed the protocol, statistical analytic

plan, and other trial documents. No interim analyses were conducted beyond assessing protocol adherence.

## Dissemination Policy

We plan to disseminate the results of the MyTEMP trial through peer-reviewed publication.

## Supplemental Material

Supplemental material for this article is available online.

## SUPPLEMENT

Supplementary content for [name], [name], [name], et al. Major Outcomes With Personalized Dialysate TEMPerature (MyTEMP) Trial: Statistical Analysis Plan of a Registry-Based, Cluster-Randomized Clinical Trial. *Can J Kid Health Dis.* 20xx; doi

[figure not shown]
**Figure 1.** Flow of hemodialysis centers (clusters) and patients in the Major Outcomes With Personalized Dialysate TEMPerature (MyTEMP) Trial

**Figure 2.** Potential transitions of patients during their observation period in the MyTEMP trial

**Appendix 1.** Bayesian analysis: Prior beliefs

[figure not shown]
**Table 1.** Characteristics of reference prior probability distributions representing prior beliefs about the primary composite endpoint benefit in the MyTEMP trial

**Figure 1.** Flow of hemodialysis centers (clusters) and patients in the Major Outcomes with Personalized Dialysate TEMPerature (MyTEMP) Triala

a No loss to follow-up is expected other than if a patient emigrates from Ontario (expected in less 0.5% of patients).

**Figure 2.** Potential patient transitions during their observation time in the MyTEMP trial

Abbreviations: \*CV, cardiovascular; ++ ICHD, in-center hemodialysis.

Patients can only enter states 2, 3 and 4 (i.e., change in modality and/or change in dialysis center) after they have remained in the new modality or center for at least 30 days. Their time in this state begins to accrue once they have met the 30-day rule.

Patients can only enter the “6. No kidney replacement therapy” state after they have remained off kidney replacement for at least 90 days. Their time in this state begins to accrue once they have met the 90-day rule.

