For both the intervention and control groups, we will report the proportion of patients' observation time spent receiving (1) in-center hemodialysis at the index center (or a center providing the same allocated temperature protocol as the index center), (2) in-center hemodialysis at a study center providing the other allocated temperature protocol ("patient crossovers"), (3) dialysis at a nonstudy center in Ontario, (4) other types of dialysis (ie, home hemodialysis, peritoneal dialysis, in-center nocturnal hemodialysis, or in-center self-care hemodialysis), (5) no dialysis due to receipt of a kidney transplant, and (6) no dialysis due to receiving palliative care or due to recovered kidney function. The aggregate proportions will be weighted by the patient's observation time. Based on our analysis of historical records, we expect  $\geq 85\%$  of the patients' observation time will be spent receiving in-center hemodialysis with the originally allocated temperature protocol.

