In the as-treated analysis, transfer to a dialysis center providing the other allocated temperature protocol (for  $>30$  consecutive days) will be treated as a time-varying exposure variable. The patient's observation time will end when they (1) switch to another type of dialysis for  $>30$  consecutive days (eg, home hemodialysis, peritoneal dialysis, in-center nocturnal hemodialysis, or in-center self-care hemodialysis), (2) transfer to a center not participating in the trial for  $>30$  consecutive days, (3) receive a kidney transplant, or (4) no longer receive any form of kidney replacement therapy for at least 90 consecutive days. These events will be treated as competing-risk events in the as-treated analysis (see section "Additional Analyses," below, for more details). In addition, for patients at a small proportion of centers that started delivering the allocated temperature protocol after the trial start date (ie, after April 3, 2017) due to delays in ethics and institutional approvals, the patients' observation time will begin after the center started delivering the allocated treatment protocol. Finally, as in the intent-to-treat analysis, we will assume all patients in a given center received hemodialysis using the temperature protocol allocated to that center; as described above in section "Adherence and Protocol Deviations," we expect  $>80\%$  of hemodialysis treatments on average will be adherent to the allocated protocol.

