## LEGEND

Black arrows: Patient transitions to terminating events (i.e., where a patient's follow-up ends).

Dash arrow: Patient crossovers between the intervention and control arms (this transition will be ignored in the intent-to-treat analysis and treated as a time-varying exposure variable in the as-treated analysis).

Dotted arrows: Patient transitions away from the allocated therapy (i.e., to dialysis centers not participating in the trial, to other types of treatments for kidney failure, and to no kidney replacement therapy). These transitions will be ignored in the intent-to-treat analysis and treated as competing-risk events in the as-treated analysis, where a patient's observation time will end when they experience any of these events.

Light grey-shaded box: The index center where a patient's observation time begins.

Dark grey-shaded boxes: Terminating events (i.e., the outcome of interest [e.g., the primary outcome or another study outcome], non-cardiovascular death [which will be treated as a competing-risk event in the primary analysis], the study end date (March 31, 2021), or emigration from Ontario.

Non-shaded boxes: Transient events (i.e., changes in treatment modality or center), where patients may move back and forth between different treatment modalities or hemodialysis centers.

The care of patients receiving hemodialysis can be complex. Patients may transition to different hemodialysis centers or to different types of treatment for kidney failure. For both the intervention and control groups, we will report the proportion of the patients' observation time spent receiving:

1. In-center hemodialysis at the index center (or a center providing the same allocated temperature protocol as the index center);
2. In-center hemodialysis at a study center providing the other allocated temperature protocol ('patient crossovers');
3. Dialysis at a non-study center in Ontario;
4. Other types of dialysis (i.e., home hemodialysis, peritoneal dialysis, in-center nocturnal hemodialysis, or in-center self-care hemodialysis);
5. No dialysis due to receiving a kidney transplant; and
6. No dialysis for at least 90 days which could represent recovered kidney function.

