The proportions will be weighted by patient's observation time on study. Based on historical data (over a 4-year follow-up period pre-dating the trial), we expect 86.7% of the patients' observation time will be spent receiving in-center hemodialysis using the originally allocated temperature protocol. We expect 2.4% of patients' observation time will be spent receiving other forms of dialysis (i.e., home hemodialysis, peritoneal dialysis, in-center nocturnal hemodialysis, or in-center self-care hemodialysis), 3.2% will be spent receiving hemodialysis at a center providing the other allocated therapy (or a center not participating in the trial), 2.6% will be spent not receiving kidney replacement (due to withdrawal or recovered kidney function), 0.5% will be spent outside of Ontario, and 4.6% will be spent living with a transplant. We expect < 1% of patients in the trial population to emigrate from Ontario during the trial period (we can ascertain any outcomes that occur before emigration), 21% to experience the

primary composite outcome, 23% to die of non-cardiovascular causes, and the remaining 55% to reach the end of the trial period.

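### The exposure table counts time in states 2–4 and 6 only after a 30- or 90-day lag, which modestly overstates time on the allocated protocol and misses deaths soon after dialysis is stopped

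*Combined protocol and SAP*

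**What the plan says.** The SAP (Adherence and Protocol Deviations) and the legend to supplement Figure 2 list six states whose shares of observation time will be reported by arm: (1) the allocated protocol, (2) a center in the other arm, (3) a non-study center, (4) another type of dialysis, (5) transplant and (6) no dialysis.

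The Figure 2 notes govern entry. States 2, 3 and 4 need at least 30 days in the new setting, and "Their time in this state begins to accrue once they have met the 30-day rule". State 6 is entered only "after they have remained off kidney replacement for at least 90 days", and again "Their time in this state begins to accrue once they have met the 90-day rule". No lag is given for transplant, for leaving Ontario, or for a return to state 1.

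State 6 is described in three ways. The SAP body has "no dialysis due to receiving palliative care or due to recovered kidney function". The list in the supplement legend has "No dialysis for at least 90 days which could represent recovered kidney function". The paragraph of expected shares attributes this time to withdrawal or recovery.

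From historical data the supplement expects 86.7% of "observation time will be spent receiving in-center hemodialysis using the originally allocated temperature protocol". The SAP body puts the expectation at 85% or more.

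The as-treated analysis uses similar thresholds. One of its end points for observation is when patients "no longer receive any form of kidney replacement therapy for at least 90 consecutive days".

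**The concern.** A persistence test can do two jobs. It can confirm that a change was lasting, and it can set the date from which the change counts. The Figure 2 notes use it for both. A patient who moves to home dialysis for good therefore has the first 30 days recorded in the state just left, and a patient who stops dialysis has the first 90 days recorded that way. Because the lags apply on leaving and none is stated for returning to state 1, the error in the on-protocol share runs one way.

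State 6 has a second problem. A patient who stops dialysis and dies before day 90 never enters it. That time, usually reported as hemodialysis at the allocated temperature, is the kind of time that the SAP body's mention of palliative care leads a reader to expect in state 6.

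At stake is a planned description of contamination and exposure. The protocol's Discussion names transfers to differently allocated centers as a way the effect could be attenuated. Run sheets are sampled from patients dialyzing at each center, so they do not show time spent elsewhere or off dialysis. The table of shares does.

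**Working it through.** **Inputs** (supplement, expected shares after the Figure 2 legend): other dialysis 2.4% (state 4); other-arm or non-participating center 3.2% (states 2 and 3); no kidney replacement 2.6% (state 6); outside Ontario 0.5%; transplant 4.6%. Lags from the Figure 2 notes: 30 days for states 2–4, 90 days for state 6.

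**Reproducing the plan's figure.** 100 − (2.4 + 3.2 + 2.6 + 0.5 + 4.6) = 100 − 13.3 = 86.7, an exact match. The shares fill 100% with no category for lag time. Of the 13.3 points, 2.4 + 3.2 + 2.6 = 8.2 (62%) lie in states with a lag; 0.5 + 4.6 = 5.1 (38%) do not.

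**Uncounted time.** If a state shows share s after lag L, and the mean counted stay is m days, each stay hides L days for every m counted. The hidden share is s × L / m. Over the lagged states:

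hidden = (5.6 × 30 + 2.6 × 90) / m = (168 + 234) / m = 402 / m percentage points.

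The documents give no stay length, so m is an assumption:

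| Mean counted stay | Hidden (points) | Share if lag time sits in state 1 | Share if lag time was dropped: 86.7 / (1 + hidden/100) |
|---|---|---|---|
| 0.5 year (182.6 days) | 2.2 | 84.5% | 84.8% |
| 1 year (365.25 days) | 1.1 | 85.6% | 85.8% |
| 1.5 years (547.9 days) | 0.7 | 86.0% | 86.1% |

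The direction is the same either way. With lag time in state 1, the share falls below 85% when 402 / m > 86.7 − 85 = 1.7, that is when m < 402 / 1.7 ≈ 236 days.

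**Deaths soon after stopping.** These patients never enter state 6, so the formula above misses them. The supplement expects 23% to die of non-cardiovascular causes. The protocol's Table 2 gives 31,314 patient-years, a mean of 31,314 / 15,500 = 2.02 years, or 31,314 / 13,500 = 2.32 years with the SAP's patient count. Assume a fraction w of those deaths follow a stop of dialysis by d days. The added share is 23% × w × d / mean follow-up:

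- w = 10%, d = 7, 2.32 years: 0.23 × 0.10 × 7 / 847 = 0.02 points.
- w = 50%, d = 30, 2.02 years: 0.23 × 0.50 × 30 / 738 = 0.47 points.

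At a one-year stay and the upper value, the share would be 86.7 − 1.10 − 0.47 = 85.1%. At that upper value the crossing point moves to 402 / (1.7 − 0.47) ≈ 327 days.

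**The case against.** Several objections have force.

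- **Scope.** A reader might infer that all time off the allocated treatment is counted late. It is not: 38% of the expected off-protocol time, including transplant as the largest single share, has no stated lag.
- **Size.** The stay length is not documented. Nor is it stated that the historical 86.7% was built with these lags. Shares summing to 100% do not show it, because shares built from actual change dates would also sum to 100%. Lag time in a move between two off-protocol states stays off protocol, so crediting all of it to state 1 is the upper case for a given m.
- **Consequence.** A reader might infer that this share decides whether a null result means the temperature failed or was not received. The documents do not support that. Programmed dialysate temperature comes from the run-sheet samples and is reported by arm with confidence intervals. Intent-to-treat ignores these transitions and takes precedence over as-treated. No decision hangs on 85%. As an illustration, with log-linear dilution a true hazard ratio of 0.80 would become 0.824 at 86.7% exposure, 0.826 at 85.6% and 0.828 at 84.5%.
- **Rationale.** The lag is disclosed, applies to both arms, and guards against a registry that may capture temporary switches. The legend's label for state 6 also states the 90 days.

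These points limit the scope and size of the concern. They do not remove the bias: screening out brief switches requires a persistence test, but not discarding the days already spent in the new state once the test is passed.

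A reader might also want an as-treated sensitivity run that ends exposure at the last session in patients who die after stopping. That would truncate exposure only in those who die, so it selects on the future outcome and should not be added.

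**Conclusion.** The point holds for states 2, 3, 4 and 6. Applied as written, the rule biases the reported share of time on the allocated protocol upward and leaves deaths within 90 days of stopping dialysis out of a state that the SAP body says includes palliative care. The three descriptions of state 6 do not agree.

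The overstatement is modest, about one percentage point at an assumed one-year mean counted stay. On counted departures alone, the share drops below 85% only if that stay is under about 236 days. Applying any of this to the 86.7% assumes that the historical figure used the same lags, which the documents leave open; they do not establish that the stated expectation is wrong. The affected figures are the exposure shares. The intent-to-treat results and the run-sheet temperature data are untouched.

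**What to change.** 1. In the descriptive exposure table, keep the 30- and 90-day tests only to confirm that a change was lasting, then assign time from the recorded date of change. No outcomes are compared in this table, so back-dating creates no immortal time.
2. Count time from a recorded stop of dialysis to death as off dialysis even when it is under 90 days. Tie this to a recorded stop, so that ordinary gaps between sessions before a death are not reclassified.
3. Use one definition of state 6 in the SAP body, the legend's list and the paragraph of expected shares.
4. State whether the 86.7% and the 85%-or-more expectation were computed with the lags; if so, restate them on the new basis.

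The cost is SAP wording and a small change to derivation code. Applying the 30- and 90-day tests already requires the dates of change. The likely downside is a slightly less favorable stated share.
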